All study participants will receive the Muse S^{TM} Headband system at study entry and will be asked to utilize it at least 4 times per week for a minimum of 10 minutes each time over a period of 3 months (12 weeks). They will be followed for a period of 6 months (3 months of treatment and 3 months post treatment) according to the schedule below.

We arable for LC

Pls: [name]; [name], PhD

Mayo Clinic - NCT05199233

	Consent /screen /baseline	Treatment Phase				Follow up Phase
Visit No.	1	2	3	4	5	6
Visit Type	Face to Face	Phone	Phone/ Email	Phone/ Email	Face to Face/ Phone/ Email	Face to Face/ Phone/ Email
Visit Days	0	2	30	60	90	180
Consent/Screening/						
Enrollment						
Informed Consent	X					
Inclusion/Exclusion	X					
Demographic and History	X					
Form	Λ					
Safety Data						
Depression	X		X	X	X	X
Adverse Events ¹			X	X	X	X
Concomitant Medication ²	X		X	X	X	X
Intervention						
Instructions for Muse-S TM & Fitbit [®] Tracker	X					
Muse-S TM use	X		X	X	X	
Fitbit [®] Tracker		X			X	X
Outcome						
CBS Cognitive Tests	X				X	X
Anxiety	X		X	X	X	X
Cognition Function	X		X	X	X	X
Emotional Distress	X		X	X	X	X
Quality of Life	X		X	X	X	X
Resilience	X		X	X	X	X
Self-Efficacy	X		X	X	X	X
Sleep	X		X	X	X	X
Stress Scale	X		X	X	X	X
Satisfaction Survey						X
End of Study Forms						X

^{1 =} For visit 5 & 6 only serious adverse events will be newly collected; 2 = For visit 5 & 6, only newly added concomitant medications will be collected

Study Visit Windows:

Each visit will have a window from the midpoint of the prior visit to the midpoint of the latter visit.

Data Collection:

Mayo Clinic - NCT05199233

Subjects will have the options of completing study surveys/questionnaires online via email link to REDCap prior to study visit. If not completed by the time the study visit takes place, the coordinator can provide the iPad digital version of the survey/questionnaire to the subject for the in-person visits or can interview the patient via phone for the telephone visits. If a subject misses a visit, the study staff will connect with the subject to collect what study data is appropriate through a simple virtual connection (email redcap surveys or telephone interview of surveys). Data Collection in this study will utilize REDCap⁴. All other data collection will be entered directly into a password protected system.

Assessments:

Safety:

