• Depression: The PHQ-2^{5,6} is a validated and frequently used self-report measure of depressive symptoms comprising of 2 questions, which were derived from the PHQ-9^{7,8}.

Outcomes:

- Demographics Form: This form collected demographic and other lifestyle history of the research subject.
- Quality of Life: Will be measured using the *Linear Analogue Self-Assessment (LASA)*⁹⁻¹¹. This is a six-item measure of quality of life (QOL), in which QOL is conceptualized as a multidimensional construct with five domains (physical, functional, emotional, spiritual, and social). This data will be collected at screen (prior to any treatment), day 30, day 60, day 90 end of treatment, and day 180 end of study (3 months post last treatment).
- Anxiety: State-Trait Anxiety Inventory (STAI-Y1)¹²⁻¹⁶ This 20-item self-report measure indicates the intensity of feelings of anxiety; it distinguishes between state anxiety (a temporary condition experienced in specific situations) and trait anxiety (a general tendency to perceive situations as threatening). It uses a 4-point visual analog scale, and the participant indicates how they feel in the moment (1 = not at all to 4 = very much so).
- Stress: Will be evaluated through the *Perceived Stress Scale (PSS)*^{17,18}. The PSS is a 10-item Likert scale that measures global life stress by assessing the degree to which experiences are appraised as uncontrollable or unpredictable. Scores can range from 0 to 40, with higher scores indicating greater perceived stress. Reliability is reported as 0.85, with Cronbach alphas ranging from 0.75-0.86.
- Resilience: Will be evaluated through the *Connor-Davison Resilience Scale 10 (CD-RS10)*¹⁹. This is a 10-item, Likert scale, validated scoring system. The CD-RS10 is a reliable means of assessing resilience and is most often used in medical and/or disaster studies²⁰.

Sleep Quality:

(ASCQ-Me® v2.0 Sleep Impact - Short Form²¹) is an effective instrument used to measure the impact sleep has on overall health in adults. The ASCQ-Me Sleep Impact SF is equivalent to the PROMIS Sleep Disturbance and Sleep-Related Impairment Surveys except the scoring is reversed.²¹ The PROMIS surveys indicate greater symptom burden as the score goes higher and the ASCQ-ME survey indicates better health as the score goes up. The Sleep Impact Scale consists of 5-item, likert scale, validated, scoring system.²² The 5 questions focus on experiences in the prior 7 days.

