Self-efficacy (Short Form 4a – 4 items)²³: This PROMIS Self-efficacy Scale defines self-efficacy as confidence in one's ability to successfully perform specific tasks or behaviors. It assesses confidence in one's ability to successfully perform specific tasks or behaviors related to one's health in a variety of situations. Each item on the measure is rated on a 5-point scale (1=I am not at all confident; 2=I am a little confident; 3=I am somewhat confident; 4=I am quite confident; 5=I am very confident)

Wearable for LC PIs: [name]; [name], PhD Mayo Clinic - NCT05199233

- Emotional Distress: Adapted from the Emotional Distress-short form 7a (7 items)²³. The PROMIS Anxiety item banks assess self-reported fear (fearfulness, panic), anxious misery (worry, dread), hyperarousal (tension, nervousness, restlessness), and somatic symptoms related to arousal (racing heart, dizziness). Anxiety is best differentiated by symptoms that reflect autonomic arousal and experience of threat. Only one behavioral avoidance item is included in the adult item bank; therefore, behavioral fear avoidance is not fully evaluated. The anxiety measures are universal rather than disease specific. The original adult short form (7a), which is being used in this study was constructed by the domain team with a focus on representing the range of the trait and also representing the content of the item bank. Domain experts reviewed short forms to give input on the relevance of each item. Psychometric properties and clinical input were both used and likely varied in importance across domains. Each item on the measure is rated on a 5-point scale (1=never; 2=rarely; 3=sometimes; 4=often; and 5=always) with a range in score from 7 to 35 with higher scores indicating greater severity of anxiety. The original form instructed participants to think about the past seven days, but for purposes of this study, we will reword the question to focus on the current time ('now').
- Cognitive Function (short form 6a 6 items)²³: The PROMIS Cognitive Function and Cognitive Function Abilities Subset item banks assess patient-perceived cognitive deficits. Facets include mental acuity, concentration, verbal and nonverbal memory, verbal fluency, and perceived changes in these cognitive functions. The extent to which cognitive impairments interfere with daily functioning, whether other people observe cognitive impairments, and the impact of cognitive dysfunction on quality of life are also assessed.

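### New non-serious adverse events starting in roughly the last month of treatment are not collected, because footnote 1 gives the end-of-treatment visit the same serious-only limit as the follow-up visit

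*Combined protocol and SAP*

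**What the plan says.** The visit schedule under Study Design and Methods marks adverse events at visits 3, 4, 5 and 6 (days 30, 60, 90 and 180). Its first footnote qualifies the last two: "For visit 5 & 6 only serious adverse events will be newly collected". Visits 3 and 4 carry no such limit.

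The same schedule sets visits 2 to 5 under Treatment Phase and only visit 6 under Follow up Phase. Muse-S use is marked at visit 5 and not at visit 6. The Quality of Life entry under Outcomes describes the two time points as "day 90 end of treatment, and day 180 end of study (3 months post last treatment". The Methods text gives the length of treatment as "over a period of 3 months (12 weeks"), which can be read as 84 or about 90 days. Under Study Visit Windows: "Each visit will have a window from the midpoint of the prior visit to the midpoint of the latter visit".

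The Safety part of the Assessments section describes only the PHQ-2. The Data Analysis Plan does not mention adverse events.

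**The concern.** Visit 5 looks back over the final stretch of treatment, yet it is handled like the visit three months after treatment. A non-serious event that first appears after visit 4 has no place in the record. The plan itself chose to record non-serious events during treatment at visits 3 and 4. That collection stops one visit early, and no reason is given.

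At stake is a complete on-treatment record of non-serious events. Use of the device will be summarised over all 12 weeks. A tolerability description over the same period could not include new minor events from its last part, and a late fall in use could not be set beside such events.

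**Working it through.** The documents state no figure for adverse event coverage, so there is none to reproduce. The check is day arithmetic on the schedule.

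**Inputs**
- Visit days 30, 60, 90 and 180 for visits 3 to 6 (visit schedule).
- Last contact that collects all new adverse events: visit 4, day 60 (adverse event row with footnote 1).
- End of treatment: day 90 (Quality of Life entry), or day 84 = 12 × 7 (Methods).
- Window limits: midpoints between neighbouring visits (Study Visit Windows).

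**Nominal gap** = end of treatment − day of visit 4
- 90-day reading: 90 − 60 = 30 days; 30/90 = 33%.
- 84-day reading: 84 − 60 = 24 days; 24/84 = 29%.

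**Variation between participants**
- Visit 4 window: (30 + 60)/2 = 45 to (60 + 90)/2 = 75.
- 90-day reading: from 90 − 75 = 15 to 90 − 45 = 45 days.
- 84-day reading: from 84 − 75 = 9 to 84 − 45 = 39 days.

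These are limits for one participant whose visit 4 falls at the edge of its window. They are not estimates for the trial.

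**Reach of visit 5 if it collected all new events**
- Visit 5 window: (60 + 90)/2 = 75 to (90 + 180)/2 = 135.
- Latest visit: 135 − 90 = 45 days after treatment, or 135 − 84 = 51. Without onset dates, those days would mix with treatment days.
- Earliest visit: 90 − 75 = 15 treatment days still uncovered (17%), or 84 − 75 = 9 (11%).

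**What visit 5 still records**
- Serious events, the PHQ-2, Fitbit data and newly added medications (the last by footnote 2). Events already known at visit 4 may also be followed, since the footnote restricts only new ones.
- The outcome scales. LASA has a physical domain. The item bank behind the distress form includes "somatic symptoms related to arousal (racing heart, dizziness").
- The scales have short or current reference periods where one is stated. For state anxiety, "the participant indicates how they feel in the moment"; for distress, "we will reword the question to focus on the current time ('now"); for sleep, "The 5 questions focus on experiences in the prior 7 days".

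A new medication or a worse LASA physical score can hint at an event. Neither records what happened or when it began. A new headache for which no new medicine was taken, for example, might leave no identifiable trace.

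**The case against.** The strongest reply is that this is a deliberate choice for a low-risk headband. Both schedule footnotes pair visits 5 and 6 and reduce collection in both rows. There is no safety aim, endpoint or adverse event summary, all analyses are declared exploratory, and no section promises non-serious collection through day 90. In one arm, overlap with post-Covid symptoms limits attribution in any case. Most of this stands. It fixes the weight of the point as minor, and the documents do not contradict themselves in the strict sense. It does not fill the gap: no rationale is stated, and visits 3 and 4 show that non-serious events were thought worth recording on treatment.

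A second reply is that visit 5 already captures much through new medications, the PHQ-2 and the scales. Staff also contact participants whose device data are not arriving (Adherence to Intervention). These do shrink the loss. However, the documents do not say that events are recorded at such contacts, and none of these sources is an event record.

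Three stronger readings are tempting and should not be drawn.
- A reader might infer that up to half of treatment is uncovered. That needs visit 4 on the earliest day of its window, day 45, and describes one participant at the extreme.
- A reader might infer that a number of events is lost. The documents give no event rate, so days uncovered cannot be turned into a count.
- A reader might extend the complaint to footnote 2. The analysis plan uses no medication data and the medication form is not shown, so the documents do not support that as a finding.

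**Conclusion.** The point holds as a minor gap in completeness. Under the plan as written, new non-serious adverse events with onset between visit 4 and the end of treatment are not collected: nominally 30 of 90 treatment days (33%), or 24 of 84 (29%), varying by participant with the visit window. This rests on the plain reading of footnote 1, on visits 4 and 5 being held on their nominal days, and on no unshown procedure collecting such events.

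A reader might go further and infer that a planned result is compromised. The documents do not support this: no adverse event analysis is planned, and the primary adherence outcome comes from device data. Nor is safety information at visit 5 absent, since serious events and the partial traces remain.

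**What to change.** Reword footnote 1 so that the serious-only limit applies to visit 6 alone. Have visit 5 collect all new adverse events since visit 4, each with an onset date, so that events starting after the end of treatment can be separated from on-treatment events when the visit is held late.

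The cost is one footnote edit, an onset date for each event, and a few more minutes of data entry per participant. The adverse event row is already marked at visit 5, so no contact is added and no planned analysis changes.

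One limit remains. If visit 5 is held at the start of its window, up to 15 of 90 treatment days (9 of 84) would still follow the last collection of non-serious events.

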Please note: Patients must have access to an iOS or Android capable device to take part in this study in order to interact with the Muse-STM Headband system.

Treatment phase:

During the first three months of study, participants will be asked to complete the online study intervention using the Muse-STM headband. Participants will be contacted via telephone and online (REDCap) for study visits at day 2, 30 and 60. At day 90, they will be asked to return to the clinic for an in-person visit (telephone and online will be alternatives).

Study Follow-Up Visits:

The study will consist of a 6-month visit post baseline (3-month post end of intervention). Participants will be asked to complete an in-person visit, if possible (telephone and online will be the alternative), which will include a second POCUS exam.

Subject Information

Target accrual: We plan to recruit 80 patients diagnosed with Post-Covid Syndrome at Mayo Clinic with the intent of enrolling 60 to study.

Subject population: A total of 60 patients diagnosed with Post-Covid Syndrome at Mayo Clinic who meet the following study criteria:

Inclusion Criteria:

- 1. 18 years of age or older at time of consent
- 2. Identified with Post-Covid Syndrome (PASC) at Mayo Clinic Rochester:

Wearable for LC

PIs: [name]; [name], PhD

Mayo Clinic - NCT05199233

- 3. Not pregnant by subject self-report at time of consent
- 4. Have the ability to provide informed consent
- 5. Have the ability to complete all aspects of this trial
- 6. Have access to an iPhone, iPad, or Android device
- 7. Have no contraindicating comorbid health condition which would interfere with the proper use of the Muse-STM system, as determined by the clinical investigators

Exclusion Criteria:

- 1. Used an investigational drug within the past 30 days
- 2. Anyone that is not on a stable dose of medication for anxiety, depression or sleep
- 3. Currently (within the past 3 weeks) been practicing mindfulness training on a weekly/regular basis
- 4. Currently (within 3 weeks) has been enrolled in another clinical or research program which intervenes on the patients' QOL, or stress
- 5. An unstable medical or mental health condition as determined by the physician investigator

Data Analysis

Data Analysis Plan:

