Demographic characteristics are described using mean and standard deviations or frequencies and percentages based on the type of variable. For the primary aim of assessing feasibility, descriptive statistics and graphical displays will be presented for data obtained on frequency and duration of use over the 12 weeks of treatment. A linear mixed model with repeated measures for each time point that stress and sleep were taken will be utilized to estimate the association between the number of sessions spent using the Muse-STM with the stress and sleep level outcome. As secondary outcomes, the results of the LASA, resilience, coping, and cognitive testing will be analyzed using similar mixed models. In all cases, results will be summarized using point estimates and corresponding 95% confidence intervals. Given the number of outcomes assessed, all analyses will be considered exploratory.

Endpoints:

Primary Hypothesis:

a) Post Covid patients enrolled in this study will find the Muse-STM Headband system easy to use and will use it per protocol.

Secondary Hypotheses:

- a) Stress score will be lower and sleep score will be improved when compared to the baseline measures for those who use the Muse-STM system as directed.
- b) As the use of the Muse-STM system increases, QOL, resilience and coping will improve.

References

1. Ninifaggi F. Physician engagement: mindfulness as part of the pandemic solution. Elsevier Connect. https://www.elsevier.com/connect/physician-engagement-mindfulness-as-part-of-the-pandemic-solution. Updated 11 May 2020. Accessed 11 June 2020, 2020.

- 2. Mayo Clinic Staff. Stress Management. Healthy Lifestyle Web site.

 https://www.mayoclinic.org/healthy-lifestyle/stress-management/in-depth/stress-relievers/art-20047257. Updated 12 March 2019. Accessed 01 June 2020.

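### The midpoint window rule gives visit 5, labelled end of treatment, days 75 to 135 and leaves visit 6 with no upper limit

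*Combined protocol and SAP*

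**What the plan says.** The Study Visit Windows section contains a single rule: "Each visit will have a window from the midpoint of the prior visit to the midpoint of the latter visit". The visit schedule puts visits 1 to 6 at days 0, 2, 30, 60, 90 and 180, with visit 5 in the treatment phase and visit 6 in follow-up. The Quality of Life entry under Outcomes labels the last two occasions "day 90 end of treatment, and day 180 end of study (3 months post last treatment". The Treatment phase section sets the target for visit 5: "At day 90, they will be asked to return to the clinic for an in-person visit", with telephone and online contact as alternatives.

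Treatment length is stated in two ways. The Methods section asks for device use "over a period of 3 months (12 weeks", and the Data Analysis Plan refers to "data obtained on frequency and duration of use over the 12 weeks of treatment". The visit labels, by contrast, put the end of treatment at day 90.

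For missed visits, the Data Collection section says: "If a subject misses a visit, the study staff will connect with the subject to collect what study data is appropriate". It gives no time limit.

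In the schedule, the row "CBS Cognitive Tests" is marked at visits 1, 5 and 6 only. The survey outcomes are marked at visits 1, 3, 4, 5 and 6.

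The Data Analysis Plan specifies linear mixed models with repeated measures for stress and sleep, and similar models for the other outcomes, including cognitive testing. It does not say whether time enters as the scheduled visit or as the actual day of assessment.

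**The concern.** A midpoint rule behaves well when visits are evenly spaced. Here the gap between visits triples, from 30 to 90 days, exactly where treatment gives way to follow-up. The visit that should mark the end of treatment therefore gets a window that lies mostly on the follow-up side. Visit 6 has the mirror problem. It is meant to describe the state three months after treatment, but its window opens 45 days after day 90 and never closes.

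The interpretation of the visit 5 and visit 6 scores is at stake. If nominal visit is used as time, a score from well after the requested-use period is averaged with scores from its end, and the result is presented as one time point. Whether this flatters or dilutes the apparent change depends on whether any effect fades or persists, which the study cannot assume. The surveys also have visits 3 and 4 within the treatment phase. CBS has only visit 5 there, so any result described as its change over treatment rests on that one window.

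**Working it through.** **Inputs.** Visit days 0, 2, 30, 60, 90, 180 (visit schedule). Window rule (Study Visit Windows). End of treatment at day 90 (Quality of Life entry) or at 12 weeks (Methods; Data Analysis Plan), that is 12 × 7 = day 84. The documents print no numeric windows, so there is no stated figure to reproduce.

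**Formula.** The rule is read as the midpoint between adjacent scheduled days: lower limit = (previous day + own day)/2; upper limit = (own day + next day)/2.

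**Midpoints.** (0+2)/2 = 1; (2+30)/2 = 16; (30+60)/2 = 45; (60+90)/2 = 75; (90+180)/2 = 135.

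**Windows.**

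| Visit | Day | Window | Relative to target |
|---|---|---|---|
| 2 | 2 | 1 to 16 | -1/+14 |
| 3 | 30 | 16 to 45 | -14/+15 |
| 4 | 60 | 45 to 75 | -15/+15 |
| 5 | 90 | 75 to 135 | -15/+45 |
| 6 | 180 | from 135 | -45/no limit |

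Neighbouring windows share their boundary day, so a day-135 score fits both visit 5 and visit 6.

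**Permitted lateness at visit 5.** The window is 135 - 75 = 60 days wide.
- Treatment ends on day 90: 135 - 90 = 45 days late at most; 45/60 = 75% of the window lies after treatment.
- Treatment ends on day 84: 135 - 84 = 51 days late at most; 51/60 = 85% of the window lies after treatment.

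**Effect of a symmetric limit.** Using the half-width that the rule already allows before day 90, the upper limit is 90 + 15 = day 105. Maximum lateness falls from 45 to 15 days after day 90, or from 51 to 105 - 84 = 21 days after day 84.

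**Does other text tighten the rule?** No. The day-90 clinic visit is a target. The missed-visit text has no deadline. The Data Analysis Plan gives no analysis window.

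**The case against.** The strongest reply is that no planned analysis is shown to suffer. The Data Analysis Plan names no day-90 contrast, the secondary outcomes are changes over time, and secondary hypothesis (a) compares with baseline without naming a visit. The rule stands in the methods, next to Data Collection, so it may be only a scheduling tolerance. A midpoint rule also has a merit: it assigns nearly every assessment to its nearest visit and discards nothing. All of this stands, and it is why the consequence is stated as conditional on the window being used to assign scores. It does not remove the point, because the plan leaves that use open and does label visit 5 as end of treatment.

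Late visits may also be rare. Surveys can be completed through an emailed link before the visit, telephone is available, and CBS is self-administered on the web. This stands too: the documents give no distribution of visit timing.

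On visit 6, the Methods describe six months of follow-up, so the study is not open-ended in intent. That is a nominal duration, however, and not a window.

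A reader might infer that sleep is the outcome most affected, because "The 5 questions focus on experiences in the prior 7 days". The documents do not support this. The STAI asks about feelings at the moment of completion and the Emotional Distress form is reworded to the present, so both leave the requested-use period sooner than a seven-day measure does.

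**Conclusion.** The point holds as a low-severity weakness in a stated rule. Visit 5 may be recorded up to 45 days after day 90 (51 days after day 84), against 15 days late for visits 3 and 4, and visit 6 has no upper limit. CBS is the most exposed outcome.

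This rests on two assumptions: that midpoints are taken between scheduled days (if actual visit dates were meant, the limits would move by participant), and that the window decides the time point under which a score is analysed.

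A reader might go further in three ways that the documents do not support.
- That end-of-treatment results will in effect describe the middle of follow-up. Day 135 is the last permitted day, and how many scores would fall near it cannot be computed.
- That late scores are off-device scores. Under Subject Retention participants keep the headband, and continued use at month 6 is an exploratory aim. Late scores fall outside the requested-use period, but not necessarily outside use.
- That the main result is compromised. The primary outcome comes from server records of the time and duration of each session and does not depend on visit dates. The plan also declares all analyses exploratory.

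**What to change.** 1. Keep every survey and CBS score, and enter the actual assessment day in the mixed models. This alone settles the modelling part of the concern.
2. For any result reported as end of treatment, limit visit 5 to a symmetric window such as days 75 to 105. Give visit 6 a lower and an upper limit around day 180, so that no day belongs to both visits.
3. Reconcile the 12-week statement of treatment length with the day-90 label when defining that window. Days 75 to 105 are symmetric about day 90 but not about day 84.

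The cost is one paragraph of protocol and SAP wording, with no new data and no change to participant contact. Using actual day means the SAP must also state how time enters the model. A few late scores lose the day-90 label but stay in the models. The limit reduces the problem without removing it, since up to 15 days of lateness (21 on the 12-week reading) would still be accepted.
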